7.26 Other Study Procedures

This section is not applicable.

7.27 Appropriateness of Measurements

The neurocognitive and developmental assessments are intended to gauge which domains can be accurately measured, with which specific tools, despite the considerable behavioral and cognitive challenges in Sanfilippo syndrome. The evaluation of these domains and the analysis of CSF, serum, and urine biomarkers may provide the pivotal data necessary to inform the clinical assessments and biomarkers used in possible future Sanfilippo syndrome ERT trials.

8 STUDY ACTIVITIES

Patients who participated in Study HGT-SAN-055 through Week 26 and completed the EOS evaluations may be eligible for enrollment in this open-label extension study. Informed consent (and assent, if applicable) must be obtained prior to performing any study related procedures that are specific to HGT-SAN-067. Informed consent may be obtained anytime from Week 20 in HGT-SAN-055. This would allow a patient to have a nonfunctional IDDD replaced or revised prior to the first rhHNS dose in HGT-SAN-067.

8.1 Screening Visit/Study Start Visit

All Screening assessments for this study are to have been performed during the Week 26 EOS procedures in HGT-SAN-055 (ie, 30 [\pm 7] days after the last rhHNS administration). If less than 60 days have elapsed since completion of the EOS assessments for HGT-SAN-055, and the start of HGT-SAN-067, the assessments detailed in this Screening visit do not need to be repeated. The Baseline visit for this study will be the first day the patient received their first dose of rhHNS in the HGT-SAN-055 Study.

If more than 60 days have elapsed following the HGT-SAN-055 EOS procedures, patients will be evaluated for enrollment in HGT-SAN-067 on a case-by-case basis by the Investigator. A decision about enrollment will be made following discussion with the Medical Monitor. If the patient is enrolled, the following assessments are to be repeated within 30 days prior to the first scheduled intrathecal rhHNS dose:

- Physical examination
- Height and weight
- Head circumference
- ECG
- Vital signs
- Hematology
 - Leukocyte pellet preparation to be used for additional disease-related laboratory studies, including possible assessment of cross-reactive immunologic material (if this is not collected at baseline, it can be collected at any subsequent pre-dosing time point)
- Serum chemistry
- Pregnancy testing (for post menarche premenopausal females only)
- Urinalysis
- Urine heparan sulfate and heparan sulfate derivatives
- Plasma and serum heparan sulfate and heparan sulfate derivatives
- Anti-rhHNS antibody testing
- General anesthesia: administration of anesthesia will be given prior to the following assessments:
 - ABR
 - MRI of the head
- Neurological examination (performed prior to the administration of anesthesia)

- Full Neurodevelopmental assessments, including Vineland Adaptive Behavior Scales, Second Edition (VABS-II; all assessments performed prior to the administration of anesthesia)
- CSF sample collection (chemistry, cell count, heparan sulfate and heparan sulfate derivatives, and other MPS exploratory biomarkers) via the IDDD
- Children's Sleep Habits Rating Scale
- CHQ-50
- CHQ-87
- ITQOL
- Concomitant medications, therapies, and procedures
- AE assessments

8.2 Treatment: Drug Administration and Weekly Assessments

Patients will receive rhHNS IDDD monthly (Q4W), on Day 2 (± 2 days), Week 1.

Patient assessments for safety, biochemical, and neurological baseline measures (Day 1, Week 1) will occur on the day before the first IT injection. Note: Day 1 assessments may be performed on the same day as the administration of study drug (Day 2). This can occur if it is feasible for the patient to arrive at the study site early in the day, and if it is deemed clinically appropriate by the Investigator. If the procedures on Day 1 and Day 2 are combined in this way, the assessments will be recorded as occurring on Day 2.

CSF samples will be obtained from these patients on Day 2, immediately prior to the first IT study drug injection. Note: Patients will not receive study drug if the pre-dose CSF contains >100 WBC per cubic millimeter.

8.2.1 Week 1

8.2.1.1 Day 1 (Pre-treatment) Assessments Performed Prior to Each Dose

- Physical examination
- Height and weight
- Vital signs
- Hematology
- Serum chemistry
- Urinalysis
- Pregnancy testing (applicable females only)
- Neurological examination (performed prior to the administration of anesthesia and the rhHNS IT injection)
- Concomitant medications, therapies, and procedures
- AE assessments

Note: If the HGT-SAN-055 EOS (or HGT-SAN-067 Screening) assessments were performed within 7 days of first intrathecal rhHNS treatment in this study, the pre-treatment assessments described in this section do not need to be completed prior to the first treatment in study HGT-SAN-067.

DAY 1 (PRE-TREATMENT) ADDITIONAL ASSESSMENTS PERFORMED AT MONTHS 12, 24, 36, AND 54

- Head circumference
- Visual and hearing assessments
- Urine heparan sulfate and heparan sulfate derivatives
- Plasma and /or serum heparan sulfate and heparan sulfate derivatives
- Anti-rhHNS antibody testing
- ABR
- MRI of the head
- Full neurodevelopmental testing, including VABS-II (performed prior to the administration of anesthesia and the rhHNS IT injection)
- Children's Sleep Habits Rating Scale
- Child health questionnaire-50
- Child health questionnaire-87
- Infant toddler QOL Questionnaire

8.2.1.2 Day 2 (± 2 days) Assessments and Administration of rhHNS

Patients may be discharged from the clinical site 8 hours after dosing, if deemed stable by the Investigator.

- Physical examination
- ECG (performed following IT study drug injection)
- Vital signs
- CSF sample collection (obtained prior to IT study drug injection)
- rhHNS IT injection (Day 2 ± 2 days)
- Neurological examination
- Concomitant medications, therapies, and procedures
- AE assessments

The neurological exam should not occur sooner than 4 hours after study drug administration or before the patient has fully recovered from any anesthesia administered for the dosing, whichever occurs later.

8.3 End of Study/Early Termination Procedures: Month 55

Patients who complete the study or who discontinue prior to the end of the study, will have EOS assessments performed 30 (± 7 days) after their last dose of rhHNS.

Patients who discontinue or are withdrawn prior to study completion will be asked to participate in the EOS procedures at the time of discontinuation. Participation in these EOS procedures will be strongly encouraged, but is voluntary for those patients electing to discontinue from the study. Note: Scheduled removal of the IDDD will be required at study completion with sedation or anesthesia, as required.

- Physical examination
- Height and weight
- Head circumference
- Visual and hearing assessment
- ECG
- Vital signs
- Hematology
- Serum chemistries
- Urinalysis
- Urine heparan sulfate and heparan sulfate derivatives
- Plasma and serum heparan sulfate and heparan sulfate derivatives
- Anti-rhHNS antibody testing
- ABR
- MRI of the head
- CSF sample collection
- Neurological examination
- Full neurodevelopmental testing, including VABS-II
- Children's Sleep Habits Rating Scale
- Child health questionnaire-50
- Child health questionnaire-87
- Infant toddler QOL Questionnaire
- Concomitant medications, therapies, and procedures
- AE assessments

All patients who discontinue the study early will have their IDDD removed.

Patients who withdraw or discontinue after having received fewer than 3 IT injections will not need to complete the EOS visit.

Patients who withdraw or discontinue from the study after having received 3 or more IT injections, will be asked to complete the EOS visit and undergo all the scheduled assessments.

8.4 Safety Follow-up (by Telephone or Visit) Month 56

Patients who complete the study or withdraw early will have a safety follow-up telephone call or visit 30 Days (± 7 days) after the last study visit. This will assess:

- Concomitant medications, therapies, and procedures

- AE assessments

9 QUALITY CONTROL AND ASSURANCE

Training will occur at an investigator meeting or at the site initiation visit or both, and instruction manuals (eg, laboratory manuals and pharmacy manuals) will be provided to aid consistency in data collection and reporting across sites.

Clinical sites will be monitored by Shire HGT or its designee to ensure the accuracy of data against source documents. The required data will be captured in a validated clinical data management system that is compliant with the Food and Drug Administration (FDA) 21 Code of Federal Regulations (CFR) Part 11 Guidance. The clinical trial database will include an audit trail to document any evidence of data processing or activity on each data field by each user. Users will be trained and given restricted access, based on their role in the study, through a password protected environment.

Data entered in the system will be reviewed manually for validity and completeness against the source documents by a clinical monitor from Shire HGT or its designee. If necessary, the study site will be contacted for corrections or clarifications; all missing data will be accounted for.

SAE information captured in the clinical trial database will be reconciled with the information captured in the Pharmacovigilance database.

10 PLANNED STATISTICAL METHODS

10.1 General Statistical Methodology

This is an open-label extension of study HGT-SAN-055 to evaluate the long-term safety and clinical outcomes of intrathecal administration of rhHNS in patients with MPS IIIA. The statistical methodology supporting the trial will focus on descriptive rather than inferential approaches, given the early phase and objectives of this trial.

Data will be summarized by dose group (10 mg, 45 mg, and 90 mg) with respect to demographic and baseline characteristics, efficacy variables and safety variables. Summary statistics for continuous variables will include the n, mean, standard deviation, median, minimum and maximum. Categorical variables will be summarized in a contingency table by the frequency and percentage of patients in each category. Data will be plotted to assess trends across time.

All hypothesis tests will be 2-sided and will be performed at the 0.05 level. Hypothesis testing will be viewed as exploratory. Any resulting p-values will not be regarded as a firm support for conclusions, but rather suggestive of areas of examination in future studies. In general, variables will be quantified as a change from the baseline value. The null hypothesis will be that there is no difference in the change from baseline between dose groups. Note that the baseline visit for this study will be the first day the patient received his/her IT dose of rhHNS in study HGT-SAN-055.

The primary objective of this trial is to assess the long term safety of rhHNS administration via a surgically implanted IDDD. Hence an extensive safety assessment will be performed. The safety analyses will consist of all enrolled patients. To evaluate safety, adverse experiences will be tabulated by dose group. Vital signs, electrocardiograms, serum and CSF components and chemistries, hematology, and urinalysis safety monitoring will be listed for each patient and abnormal values will be flagged. In addition, anti-rhHNS antibodies (in CSF and serum) will also be listed. No formal statistical tests will be performed on the safety parameters.

10.2 Determination of Sample Size

Since this is an extension study, sample size is determined by the number of patients who completed HGT-SAN-055 (maximum of 12 patients) and elected to continue treatment with rhHNS in this study

10.3 Analysis Populations

The analysis population consists of all eligible patients from HGT-SAN-055 who have agreed to participate in the extension study. Both safety and efficacy analyses would be performed using the above mentioned population.

10.4 Demographics and Baseline Characteristics

Patient disposition for those enrolled will be presented in a summary table using number and percentage of patients enrolled, completed or discontinued/withdrew, by dose group. The reasons for discontinuation/withdrawal will also be presented.

Demographic and baseline characteristics (eg, age, race, ethnicity, medical history, and surgical history) will be reported in summary tables.

10.5 Statistical Analysis of Pharmacokinetic Variables

Not applicable.

10.6 Efficacy, Safety, and Pharmacodynamic Evaluations

10.6.1 Primary Analyses

10.6.1.1 Safety Analysis

In general, safety assessments will be based on all assessments post-baseline. The assessment of safety will be based primarily on the frequency of adverse events, and on the frequency of clinically notable abnormal vital sign and laboratory values. Changes from baseline will be calculated by subtracting the baseline value from the post-baseline value.

All enrolled patients will be included in the safety analysis. Patients will be grouped according to the actual dose received.

No formal statistical test will be performed in the safety evaluations. Vital sign measurements, clinical chemistry, and hematology safety monitoring will be listed for each patient, and abnormal values will be flagged. These will also be summarized at each time point, including change from baseline.

Adverse events will be recorded throughout the study and at early termination. Adverse events and medical conditions will be coded using the Medical Dictionary for Regulatory Activities (MedDRA).

Adverse events will be summarized by presenting, for each treatment group, the number and percentage of patients having any adverse event, having an adverse event in system organ class, and having each individual adverse event. Note that in any given category (eg, system organ class) a patient will only be counted once. In addition, those events which resulted in death or were otherwise classified as serious will be presented in a separate listing. The incidence of treatment-emergent adverse events (new or worsened from baseline) will be summarized by system organ class, severity, type of adverse event and relationship to trial medication.

Adverse events that occur up to 30 days after the last dose of study drug will be considered “on-treatment”. Adverse events which are deemed probably, possibly, or definitely related to the device will be summarized by dose group and overall.

Laboratory data will be listed by patient and dose group. Patients with newly occurring abnormalities outside the normal range will be flagged and listed separately and summarized. Mean change from baseline values or shift tables will also be provided by dose group at each visit.

Vital signs data will be listed by patient and dose group. Furthermore, mean changes from baseline for vital sign data will be summarized for each dose group. Shift tables may be presented, utilizing reference ranges. Patients with notably abnormal values will be identified and listed separately along with their values.

Electrocardiograph assessments will be listed by patient and dose group. Mean changes from baseline for ECG data will be summarized for each dose group. Patients with any clinically significant findings and/or conduction abnormalities will be listed separately along with their values.

For those patients who fail to complete the study, the reason for discontinuation will be listed by patient and dose group.

Listings of all study safety data will be presented.

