4.3 Study Duration and Dates

The study duration will be 4 years.

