7.12.1 Restrictions on the Number of Revision and/or re-implantation of the IDDD

A non-functional IDDD can be replaced or revised twice in a 6-month period, including the time a patient was in study HGT-SAN-055. Similarly, 6 X-rays may be taken in a 6-month period (including the time in HGT-SAN-055).

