Appendix 1 Schedule of Events

HGT-SAN-067 Study Assessments for Patients Who Have Received 6 Months of rhHNS Treatment in Study HGT-SAN-055

Assessment	Screening/or HGT-SAN-055 EOS Visit ^k (Month 6 from the start of HGT-SAN-055)	Dosed every 28 (±7) days (ie, Q4W)		Months 12, 24, 36, and 54 (from the start of HGT-SAN-055)	EOS ^f Month 55 (from the start of HGT-SAN-055)	Month 56 Safety Follow-up ^j
		Pre-Tx Day 1 ^a	IT dosing Day 2 (±2)			
Informed Consent/Enrollment		•				
Physical Examination	•	•	•		•	
Height and Weight	•	•			•	
Head Circumference	•			•	•	
Visual and Hearing Assessment				•	•	
ECG	•		• ^b		•	
Vital Signs	•	•	•		•	
Hematology	•	•			•	
Serum Chemistry	•	•			•	
Pregnancy Testing ⁿ	•	•				
Urinalysis	•	•			•	
Leukocyte pellet preparation ^o	•					
Urine Heparan Sulfate and Heparan Sulfate Derivatives	•			• ^c	•	
Plasma and serum Heparan Sulfate and Heparan Sulfate Derivatives	•			• ^c	•	
Anti-rhHNS antibody testing (serum and CSF) ^l	•			•	•	
Auditory Brainstem Response (ABR)	•			•	•	
MRI of the Head	•			•	•	
CSF Sample Collection ^m	•		• ^c		• ^c	
rhHNS dosing: every 28 (±7) days ^{g, d}			•			
Neurological Examination ^h	•	•	•		•	
Full Neurodevelopmental Testing ⁱ	•			•	•	
Children's Sleep Habits Rating Scale	•			•	•	
Child Health Questionnaire-50	•			•	•	
Child Health Questionnaire-87	•			•	•	
Infant Toddler QOL Questionnaire	•			•	•	

HGT-SAN-067 Study Assessments for Patients Who Have Received 6 Months of rhHNS Treatment in Study HGT-SAN-055

Assessment	Screening/or HGT-SAN-055 EOS Visit ^k (Month 6 from the start of HGT-SAN-055)	Dosed every 28 (±7) days (ie, Q4W)		Months 12, 24, 36, and 54 (from the start of HGT-SAN-055)	EOS ^f Month 55 (from the start of HGT-SAN-055)	Month 56 Safety Follow-up ^j
		Pre-Tx Day 1 ^a	IT dosing Day 2 (±2)			
Concomitant Medications, Therapies, and Procedures	•	•	•		•	•
Adverse Event Monitoring	•	•	•		•	•

Abbreviations: ABR = Auditory brainstem response; CSF = cerebrospinal fluid; EOS = end of study ; ECG = electrocardiogram; IT = intrathecal; MRI = Magnetic resonance imaging; TX = treatment

Note: The timing of assessments is calculated from the start of HGT-SAN-055. Therefore, for example, the end-of-study visit, as presented here at Month 54, corresponds to Month 48 in HGT-SAN-067, but represents a total of 54 months of study treatment (48 months in HGT-SAN-067 + 6 months in HGT-SAN-055).

^a Week 1 only, and only performed if >7 days have elapsed since HGT-SAN-055 EOS visit assessments.

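### The protocol's adverse-event tables give once-per-patient incidence only, which says little about frequent or recurrent events over 4 to 4.5 years of treatment

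*Protocol*

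**What the plan says.** Section 10.6.1.1 of the protocol states "The assessment of safety will be based primarily on the frequency of adverse events", together with the frequency of notable vital-sign and laboratory abnormalities. It defines the AE summary, for each treatment group, as "the number and percentage of patients having any adverse event, having an adverse event in system organ class, and having each individual adverse event", with the counting rule "Note that in any given category (eg, system organ class) a patient will only be counted once". Treatment-emergent events are further broken down by severity, type and relationship.

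The same section plans a separate listing of serious and fatal events, a summary of device-related AEs by dose group and overall (without saying whether patients or events are counted), and listings of all safety data. No formal test is applied to safety.

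On duration, section 4.3 says "The study duration will be 4 years". Section 10.1 places baseline in the parent study: "Note that the baseline visit for this study will be the first day the patient received his/her IT dose of rhHNS in study HGT-SAN-055". The note to Appendix 1 accordingly counts 54 months of treatment in total. On the device, section 7.12.1 says "A non-functional IDDD can be replaced or revised twice in a 6-month period, including the time a patient was in study HGT-SAN-055".

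**The concern.** For a long-term safety extension the main AE questions are how often events happen, whether they recur, and whether the risk changes as treatment goes on. A cumulative percentage of patients, each counted once per category, answers a narrower question: whether the event ever happened. That has four consequences here.

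- **Ceiling.** For frequent categories almost every child is counted whatever the underlying rate, so dose groups look alike.
- **Unequal follow-up.** All enrolled patients are in the safety analysis (10.6.1.1), leavers are not replaced (7.25), and section 8.3 provides for patients who stop before 3 injections. A child with 3 doses and a child with about 52 weigh the same in a denominator of perhaps 4.
- **Recurrence.** A child with many device failures counts the same as a child with one, in a protocol that plans for repeated malfunction.
- **Time.** One cumulative figure cannot show whether AE risk rises or falls with continued dosing.

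**Working it through.** The protocol states no AE rate, so there is no figure of its own to reproduce. What follows is an illustration over a range of assumed rates.

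**Inputs from the protocol.** Duration T = 4.0 years (section 4.3) or 4.5 years (54 months, Appendix 1). Dosing every 28 days (6.2.1): 48 × 30.4375 / 28 ≈ 52 doses, or 54 × 30.4375 / 28 ≈ 59. At most 12 patients in 3 dose groups (5.1, 6.2). At most 2 device revisions per 6 months (7.12.1).

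**Assumptions.** Constant event rate λ per patient-year, the same for every patient; 4 patients per group (the split is not stated); full follow-up unless noted.

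**Step 1: percentage of patients counted.** P = 1 − exp(−λT).

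| λ | T = 4.0 | T = 4.5 |
|---|---|---|
| 0.05 | 18.1% | 20.1% |
| 0.1 | 33.0% | 36.2% |
| 0.25 | 63.2% | 67.5% |
| 0.5 | 86.5% | 89.5% |
| 1 | 98.2% | 98.9% |
| 2 | 99.97% | 99.99% |

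Solving for λ, 90% is reached at −ln(0.1)/T = 0.58 (T = 4.0) or 0.51 (T = 4.5), and 99% at 1.15 or 1.02.

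**Step 2: can a twofold difference be seen at T = 4.0?** The chance that two groups show the same count is the sum over k = 0 to 4 of Bin(k; 4, P₁) × Bin(k; 4, P₂).

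| Rates | Patients counted | Same count out of 4 | Expected events (16 patient-years per group) |
|---|---|---|---|
| 0.1 vs 0.2 | 33% vs 55% | 23% | 1.6 vs 3.2 |
| 0.5 vs 1 | 86.5% vs 98.2% | 54% | 8 vs 16 |
| 1 vs 2 | 98.2% vs 99.97% | 93% | 16 vs 32 |

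At T = 4.5 the last row gives 96%. The loss of contrast is confined to frequent categories.

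**Step 3: early leavers.** Three doses cover 3 × 28 = 84 days, or 84/365.25 = 0.23 years. At λ = 1 such a child is counted with probability 1 − exp(−0.23) ≈ 21%, against 98.2% for a child followed for 4 years. Both add 1 to the denominator.

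**Step 4: recurrence.** The permitted ceiling on device revisions is 2 × 48/6 = 16 in 48 months, or 2 × 54/6 = 18 in 54. A child at that ceiling and a child with one event each add 1 to an incidence row. This is a ceiling, not an expectation.

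**Step 5: sensitivity to equal rates.** If rates vary between children with a gamma distribution of shape 1 (an assumption), P = 1 − 1/(1 + λT). At λ = 1 and T = 4.0 this is 80%, against 89% at λ = 2, and the same count appears in 39% of trials. The ceiling effect is then weaker. Steps 3 and 4 do not depend on there being a ceiling.

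**The case against.** The strongest reply is that section 10.6.2.2 leaves planned analyses and presentations to the statistical analysis plan, which is not at hand, and that event counts and exposure columns are ordinary table-shell content. The once-per-category rule is the correct rule for an incidence row, and nothing in the protocol forbids adding to it. This stands in part: the plan may already contain the remedy. But the protocol is not silent. It names the AE measure and its counting rule for the primary question, and those are what need supplementing.

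A reader might infer that the percentage reaches its ceiling throughout, in all three groups. The documents do not support that. They give no rates, counting is per category, and Step 1 shows that rarer rows stay well below 100%.

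A reader might also infer that repeated events are lost. They are not. Each AE is recorded with onset and resolution dates (7.22.2.2), procedures are recorded (7.21), all safety data and serious events are listed, and device-related AEs have their own summary. With at most 12 patients the listings are readable. Recurrence is missing from the incidence tables, not from the data.

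Nor does all of safety rest on AE percentages. Vital signs and laboratory values are summarised at each time point, so change over time is absent only for AEs.

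Finally, it is tempting to argue that a comparison of event rates would detect dose differences. The protocol rules out tests on safety. With gamma (shape 1) variation between children at a mean of 1 per patient-year, a two-sided 5% conditional binomial comparison that ignores this variation rejects about 33% of the time when there is no true difference. The case for rates is descriptive only.

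**Conclusion.** The concern holds in limited form. The only AE frequency measure that section 10.6.1.1 specifies is patient incidence, without event counts, exposure or time intervals. For the any-AE row and common system organ classes, at assumed constant rates of roughly 0.5 to 1 or more per patient-year, it lies near its ceiling in small groups. At 1 against 2 per patient-year over 4 years, two groups of 4 agree in 93% of trials. That size rests on the constant, equal rate and on the assumed 4 per group; it shrinks if children differ widely. The equal weight given to early leavers, and the silence of the incidence rows on recurrence and time course, follow from the measure itself. Rarer rows keep their contrast between groups. This is a worthwhile improvement to the main safety summary, not an error that invalidates it.

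**What to change.** In section 10.6.1.1, keep the number and percentage of patients. Alongside them, and not in their place as the primary measure, add the number of events and events per patient-year of exposure, by dose group and overall, and by year of treatment. Give these for all treatment-emergent, serious, drug-related and device-related AEs, and for IDDD revisions and replacements. Show exposure for each group beside the percentages, and state whether the device-related summary counts patients or events.

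The cost is extra table columns. AE onset dates (7.22.2.2) and dosing dates and times (6.10) are already collected. The drawback is that with at most 12 patients one child with many events can dominate a group's rate, so the rate should be read beside the patient count and carry no significance test.

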6.2.1 Selection and Timing of Dose for Each Patient

Patients will check into the study center 1 day prior to IT rhHNS dosing for safety assessments, designated Day 1, on each rhHNS treatment week, and if no safety concerns exist, will receive IT administration of rhHNS on Day 2 (± 2 days). However, if feasible and there are no safety concerns in the opinion of the Investigator, the Day 1 and Day 2 assessments and dosing may be combined and performed on Day 2; if this is done the results will be recorded as Day 2. Patients will remain in the study centre for at least 8 hours following dosing with rhHNS and will be discharged from the unit when deemed clinically stable by the Investigator.

The IT injections are to be administered every 28 days (± 7 days). If a patient's IDDD becomes nonfunctional, it may be revised (partial or complete) (a maximum of twice in a 6 month period) so that the patient can remain on study (see Section 7.12 for details). In the event of a non-functional IDDD, rhHNS may be administered by LP, for up to 5 successive months (see Section 6.2.4).

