7.22 Adverse Events

7.22.1 Definitions of Adverse Events and Serious Adverse Events

7.22.1.1 Adverse Event

An adverse event (AE) is any noxious, pathologic, or unintended change in anatomical, physiologic, or metabolic function as indicated by physical signs, symptoms, or laboratory changes occurring in any phase of a clinical study, whether or not considered study drug-related. This includes an exacerbation of a pre-existing condition. Once the informed consent is signed and dated, any adverse event prior to the start of study drug must be reported.

AEs include:

- Worsening (change in nature, severity, or frequency) of conditions present at the onset of the study
- Intercurrent illnesses
- Drug interactions
- Events related to or possibly related to concomitant medications
- Abnormal laboratory values (this includes significant shifts from baseline within the range of normal that the Investigator considers to be clinically important)
- Clinically significant abnormalities in physical examination, vital signs, and weight

Throughout the study, the Investigator must record all AEs on the AE eCRF, regardless of the severity or relationship to study drug. The Investigator should treat patients with AEs appropriately and observe them at suitable intervals until the events stabilize or resolve. AEs may be discovered through observation or examination of the patient, questioning of the patient, complaint by the patient, or by abnormal clinical laboratory values.

In addition, AEs may also include laboratory values that become significantly out of range. In the event of an out-of-range value, the laboratory test should be repeated until it returns to normal or can be explained and the patient's safety is not at risk.

All adverse events should be recorded with causality assessment.

The information presented below is intended to provide issues to consider for AEs associated with intrathecal injections of rhHNS. In general, these AEs can be classified as follows:

- Adverse events due to systemic exposure to rhHNS caused by the drug diffusion from the CSF to the peripheral circulation;
- Adverse events related to the direct delivery of rhHNS to the intrathecal CSF space and meninges, and subsequent diffusion into brain parenchyma, via an intrathecal route
- IDDD-related AEs.

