10.6.1.2 Clinical Laboratory Evaluations

Descriptive summaries of clinical laboratory evaluations (hematology, serum chemistry, urinalysis) results will be presented in summary tables by evaluation visit using number of patients (n), mean, median, standard deviation, minimum, and maximum. Changes from baseline will be summarized for each post-baseline visit. The number of patients with clinically significant laboratory results or abnormal results during the study period will be presented in shift tables.

For the laboratory measurements, shift tables will be presented in terms of Low (L), Normal (N), High (H), Missing (M). High and Low measurements will be based on reference ranges provided by the laboratory at the study site.

Clinical laboratory results will also be presented in data listings.

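### The patient counts of new out-of-range laboratory values are met by chance in nearly every patient, so they separate dose groups poorly; count by CTCAE grade shift per analyte instead

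*Protocol*

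**What the plan says.** Section 3.1 of the protocol (Amendment 3) makes change in clinical laboratory tests part of the primary endpoint. Two sentences then define patient-level laboratory summaries:

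- Section 10.6.1.1: "Patients with newly occurring abnormalities outside the normal range will be flagged and listed separately and summarized".
- Section 10.6.1.2: "The number of patients with clinically significant laboratory results or abnormal results during the study period will be presented in shift tables". The shift categories are Low, Normal, High and Missing, set by laboratory reference ranges.

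Neither sentence asks for a magnitude, a duration or a confirming test. The neighbouring sentences in 10.6.1.1 do qualify what is listed separately: notably abnormal values for vital signs, clinically significant findings for ECG.

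Hematology and serum chemistry appear in section 8.2.1.1, headed "Day 1 (Pre-treatment) Assessments Performed Prior to Each Dose". Doses are given every 28 days, plus or minus 7 (section 6.2.1), and "The study duration will be 4 years" (section 4.3). Baseline lies before this study: "Note that the baseline visit for this study will be the first day the patient received his/her IT dose of rhHNS in study HGT-SAN-055" (section 10.1).

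These are not the only laboratory outputs. Section 10.6.1.1 rests safety primarily on adverse events and on clinically notable vital-sign and laboratory values. It also plans mean change or shift tables by dose group at each visit. Section 10.6.1.2 adds by-visit summaries with minimum and maximum, and listings. Adverse events are graded by CTCAE v3.0 (section 7.22.1.2, Appendix 6).

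**The concern.** A reference range leaves some healthy values outside it by construction. Apply it to a long list of analytes at every dosing visit for four years, and a patient who is merely being tested often will sooner or later have a new abnormal value. A table counting such patients then shows much the same figure in every dose group, with or without a drug effect.

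The three-category shift does not help with size. A value just above the upper limit and one more than 20 times that limit are both High. The count is descriptive, but it summarizes a component of the primary endpoint in a study with no data monitoring committee (section 11.8), so it should carry information.

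**Working it through.** The protocol states no expected false-flag rate, so there is no figure to reproduce. The check asks how often a patient with no drug effect would be counted.

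**Inputs from the protocol**
- Analytes: 8 in hematology (7.7.1) and 23 in serum chemistry (7.7.2), total 31. The pregnancy test, CK subtypes and white-cell differential are not counted.
- Panels: 4 × 365.25 / 28 = 52.2 at strict 28-day dosing, or 48 if monthly by calendar. Adding the end-of-study panel gives 49 to 53; 49 is used below. Counting from the HGT-SAN-055 baseline ("48 months in HGT-SAN-067 + 6 months in HGT-SAN-055") would add to this.
- Patients: at most 12 (section 5.1).

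**Assumptions, not in the protocol**
- Share q of no-effect values outside range: 5%, with 2.5% and 1% as sensitivity.
- Gaussian values; within-patient correlation over time 0 to 0.9; analytes independent of each other unless stated.
- New means in range at baseline and out of range at one or more later panels.

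**Formulas**
- Independent values, k analytes, m panels: 1 − (1 − q)^(k·m). One analyte, q = 5%: 1 − 0.95^49 = 0.92. A single panel of 31: 1 − 0.95^31 = 0.80.
- Correlated values: let p be the chance per analyte given an in-range baseline, from a random-intercept model. Pooled over analytes: 1 − (1 − p(1 − q))^31. For q = 5% and correlation 0.9, p = 0.151, so 1 − (1 − 0.151 × 0.95)^31 = 0.992.

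**Results over 49 panels**

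| Outside range | Within-patient correlation | Per analyte | Any of 31 |
|---|---|---|---|
| 5% | 0 | 92% | >99.9% |
| 5% | 0.5 | 60% | >99.9% |
| 5% | 0.7 | 37% | >99.9% |
| 5% | 0.9 | 15% | 99.2% |
| 2.5% | 0.5 | 39% | >99.9% |
| 2.5% | 0.7 | 23% | >99.9% |
| 2.5% | 0.9 | 9% | 93.9% |
| 1% | 0 | 39% | >99.9% |
| 1% | 0.9 | 4% | 74% |

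If analytes are also correlated 0.3 with each other (simulated, about 50 panels), the pooled figure at within-patient correlation 0.9 is about 98% for q = 5%, 89% for 2.5% and 65% for 1%.

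**What this means in 12 patients**
- Pooled: 12 × 0.992 = 11.9 patients expected to be flagged; at 93.9%, 12 × 0.939 = 11.3.
- Per analyte, assuming 4 patients per dose group (the split is not stated): 4 × 0.15 = 0.6 to 4 × 0.60 = 2.4 flagged by chance. At 37%, the difference between two groups has standard deviation √(2 × 4 × 0.37 × 0.63) = 1.4 patients, and there are 31 such tables.

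**How far a limit must move.** With independent Gaussian values and 31 × 49 = 1,519 tests, a limit at 3 SD still gives 98% pooled, and one at 4 SD gives 9%. Magnitude matters, and so does counting per analyte.

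**The case against.** A reader might infer from these figures that the laboratory safety plan cannot signal toxicity. The protocol does not support that. Its stated primary laboratory basis is clinically notable values. A sustained transaminase rise in one dose group would still appear in the by-visit summaries with their maxima, in the by-visit mean change or shift tables, in the listings, and among adverse events graded by CTCAE. With at most 12 patients, listings can be read case by case. The stopping rule in section 7.23 uses graded, related adverse events, not this flag.

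Second, the pooled any-analyte count is only one reading of the sentence in 10.6.1.1. Low/Normal/High tables are naturally built per analyte, where the rate does not saturate if values are correlated within patient. Section 10.6.2.2 leaves presentations to an SAP that was not available for this review, and the SAP may settle the unit of count. Both points stand, and they limit the finding to the patient counts.

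Third, a reader might think the repeat tests ("In the event of an out-of-range value, the laboratory test should be repeated until it returns to normal or can be explained") raise the chance further. They do not: a repeat follows an out-of-range result, and a patient whose result is a new abnormality is already flagged.

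What remains is that the reference range is the only laboratory limit the protocol fixes for these counts. It does not define clinically notable, and the sentence in 10.6.1.2 joins clinically significant results and merely abnormal ones in a single study-period count.

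**Conclusion.** The point holds for the patient counts and goes no further. Pooled over analytes, about 94% to 100% of no-effect patients meet the range criterion in most settings where ranges cover 95% or more of healthy values. The figure falls below that only with wider ranges together with very high within-patient correlation. Per analyte, the chance rate is about 15% to 60% with 5% of values outside range and within-patient correlation of 0.9 down to 0.5. That is too high to separate groups of about four patients.

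Reference-range coverage, the correlations and the group split are assumptions, because the protocol gives none of them. This is a reporting weakness in a primary-endpoint summary and worth correcting. It does not affect study conduct, and it does not make the other laboratory outputs uninformative.

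**What to change.** In sections 10.6.1.1 and 10.6.1.2:

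1. Keep the out-of-range flag for listings and for Low/Normal/High tables at each visit.
2. Make the study-period patient count per analyte and by dose group, from baseline grade to worst post-baseline CTCAE v3.0 grade (Appendix 6), and show new Grade 2 or higher.
3. Show separately the abnormalities confirmed on the repeat test that section 7.22.1.1 already requires.
4. For analytes with no CTCAE grade, keep the reference-range table but count confirmed abnormalities. By my count these are 11 of 31: hematocrit, MCH, MCHC, MCV, red-cell count, BUN, chloride, globulin, LDH, direct bilirubin and total protein.

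The cost is programming. The grading scale and the repeat tests are already in the protocol, so no new data collection is needed. The downside is that about a third of the analytes (11/31 = 35%) gain only the confirmation step. The chance rate of a new Grade 2 cannot be computed from the protocol, because it depends on each analyte's spread.
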